9.3.4. Adverse Events in Descending Order of Incidence

A table will be provided that displays AE preferred terms in descending order of incidence on the overall incidences. Only preferred terms will be included in this table (i.e., the display will not include SOC).

A similar table will be provided for severe AEs. AEs for which the assessment of severity is missing will be included in this table.

9.3.5. Severity of Adverse Events

AEs are classified by the Investigator for severity (“Mild”, “Moderate”, and “Severe”). An overall summary of TEAEs by SOC, preferred term, and severity will be presented. AEs with a missing severity will be counted as “Severe” in the summary table. A patient will be counted once for each SOC and preferred term based on the greatest severity within that SOC and preferred term, respectively.

9.3.6. Relationship of Adverse Events to Study Drug

AEs are classified by the Investigator for relationship to study drug (“Not related” and “Related”). An overall summary of TEAEs by SOC, preferred term, and relationship will be presented. AEs with a missing relationship will be counted as “Related” in the summary table. A patient will be counted once for each SOC and preferred term based on the highest relationship within that SOC and preferred term, respectively.

9.3.7. Serious Adverse Events

Any AE reported as resulting in death, immediate risk of death (life threatening), inpatient hospitalization or prolongation of existing hospitalization, persistent or significant disability/incapacity, or a congenital/anomaly/birth defect will be classified as an SAE. An SAE may also be any other medically important event that, in the opinion of the Investigator, may jeopardize the patient or may require intervention to prevent one of the other outcomes listed above. Events considered medically important, as defined in Section 15.1.2 of the protocol, are also considered to be SAEs.

All SAEs will be listed; treatment-emergent SAEs will be summarized overall by system organ class and preferred term.

9.3.8. Adverse Events Leading to Treatment Discontinuation or Withdrawal From the Study

AEs leading to treatment discontinuation or withdrawal from the study will be listed. All AEs reported on the AE log with “Was the patient terminated from this study due to this AE” as “Yes” or “Action Taken with Study Drug” with a response of “Drug Withdrawn” will be included.

9.3.9. Deaths on Study

A listing of events leading to death occurring on the study will be provided.

9.3.10. Adverse events of Special Interest

There are no specific AE outputs focusing on events of special interest. Any consideration of these will be based upon medical review of existing outputs.

9.4. Clinical Laboratory Evaluations

All laboratory evaluations will be summarized for the Safety Analysis Set, as described in the rest of this section. Data collected at local laboratories will be excluded from analysis, unless otherwise specified. All laboratory data will be provided in data listings; abnormal values relative to laboratory normal ranges and potentially clinically significant abnormalities will be identified. Laboratory evaluations taken during major surgical/rehabilitation periods will not be included in any summary but will be included in the listings and flagged.

Laboratory values of the form “<x” (i.e., below the lower limit of quantification [LLOQ]) or “>x” (i.e., above the upper limit of quantification [ULOQ]) will be imputed as “x” in the calculation of summary statistics but displayed as “<x” or “>x” in the listings.

9.4.1. Hematology and Chemistry

Hematology measurements that will be collected and summarized include: white blood cell count (WBC) and differential, red blood cell count (RBC), hemoglobin, hematocrit, and platelet count. Chemistry measurements that will be collected and summarized include: sodium, potassium, chloride, total protein, total bilirubin, gamma glutamyl transferase (GGT), aspartate aminotransferase (AST), alanine aminotransferase (ALT), alkaline phosphatase, blood urea nitrogen (BUN), serum creatinine, and glucose.

9.4.1.1. Change from Baseline

Hematology and chemistry results at baseline and post baseline visits, along with change from baseline, will be summarized with descriptive statistics by visit and for the end of study. Data from unscheduled visits will be excluded from this analysis. In the event of retests or repeat assessments at the same time point, the last non-missing evaluable measurement will be used for the purpose of analysis.

9.4.1.2. Shifts

Each patient’s laboratory values will be classified according to whether the test result is “low” (below the lower limit of normal [LLN]), “normal” (within the normal range), “high” (above the upper limit of normal [ULN]). Shift tables will be constructed based on both the minimum and maximum post baseline values for each patient. Data collected from unscheduled visits will be included in the determination of the per patient minimum and maximum values.

A separate table will be provided which summarizes the results of the shift tables in which the number and percentage of patients with a shift to low (from normal, high, or unknown) and the number of patients with a shift to high (from normal, low, or unknown) will be tabulated; percentages will be based on the number of patients at risk. The number at risk for a shift to low (high) is the number of patients whose baseline value was not low (high), including unknown, who had at least one post-baseline value. Only directions of change indicating a clinical concern will be included in this table summarizing the shifts. The direction of concern is provided in [Table 1](#).

Table 1: Direction of Change Indicating Clinical Concern for Laboratory Tests

Laboratory Test	Direction	Laboratory Test	Direction
Chemistry		Hematology	
Liver		White blood cells	Low and High
ALT/SGPT	High	Lymphocytes	Low and High
AST/SGOT	High	Neutrophils	Low and High
Total bilirubin	High	Monocytes	Low and High
GGT	High	Eosinophils	Low and High
Renal		Basophils	Low and High
Blood urea nitrogen	High	Red blood cells	Low and High
Creatinine	High	Hemoglobin	Low and High
Electrolytes		Hematocrit	Low and High
Sodium	Low and High	Platelets	Low and High
Potassium	Low and High		
Chloride	Low and High		
Other			
Glucose	Low and High		
Total protein	Low and High		

9.4.1.3. Potentially Clinically Significant Laboratory Abnormalities

Abnormal laboratory values will also be evaluated by determining the number and percentage of patients with at least one potentially clinically significant laboratory abnormality over the course of the study that also represents a worsening from baseline. The potentially clinically significant

levels are based on Grade 2 or higher thresholds from the Common Toxicity Criteria for Adverse Events (CTCAE v 4.02 2009) where possible, or were defined by Bioverativ’s Pharmacovigilance group.

Patients who have a post baseline laboratory value that meets the criteria for being potentially clinically significant but do not have a baseline value will be included in the numerator for determining the percentage of patients with an abnormality. Percentages will be based on the number of patients with at least one post baseline value for the given laboratory test. Threshold levels for potentially clinically significant laboratory abnormalities are provided in [Table 2](#) (hematology) and [Table 3](#) (chemistry). Data collected from unscheduled visits will be included in this analysis.

Table 2: Threshold Levels for Potentially Clinically Significant Hematology Abnormalities

	Low	High
Neutrophils	$<1.5 \times 10^9/L$	NA
Eosinophils	NA	$>1.6 \times 10^9/L$
Hemoglobin	$<100 \text{ g/L}$	Increase in $>20 \text{ g/L}$ above ULN
Hematocrit	$<30\%$	$\geq 60\%$
Platelet count	$\leq 75 \times 10^9/L$	$\geq 700 \times 10^9/L$

NA = not applicable

Table 3: Threshold Levels for Potentially Clinically Significant Chemistry Abnormalities

	Low	High
Liver		
ALT/SGPT	NA	$>3 \times \text{ULN}$
AST/SGOT	NA	$>3 \times \text{ULN}$
Total bilirubin	NA	$>1.5 \times \text{ULN}$
GGT	NA	$>2.5 \times \text{ULN}$
Renal		
Creatinine	NA	$>1.5 \times \text{ULN}$
Electrolytes		
Chloride	$\leq 90 \text{ mmol/L}$	$\geq 118 \text{ mmol/L}$
Other		
Glucose	$<3.1 \text{ mmol/L}$	$>8.9 \text{ mmol/L}$
Total protein	$\leq 45 \text{ g/L}$	$\geq 100 \text{ g/L}$

NA = not applicable, ULN = upper limit of normal

9.4.2. Urinalysis

These assessments were not performed in this study.

9.4.3. Incidence of Inhibitor Development

All the analyses in this section will be presented for the Safety Analysis Set. All analyses of, and derivations based upon, inhibitor test results are performed using the Nijmegen Inhibitor Fc assay test. In the event of a positive test, a second, plasma derived (PD) test will be performed. These PD test results will be listed only.

9.4.3.1. Endpoint Definition

A positive inhibitor occurs where a patient has a value ≥ 0.6 Bethesda Units (BU/mL) confirmed on re-testing at least 2 weeks later. See Section 5.1.2.4 for exact definition. Both tests must be performed by the central laboratory. Results from blood samples collected during surgical/rehabilitation periods for the purpose of determining the presence of an inhibitor will be included in this analysis. Inhibitor test data will be listed for all patients and separately for patients with positive inhibitors.

9.4.3.2. Primary Analysis

The primary analysis of overall incidence of positive inhibitor formation, is based on all patients who have reached at least 10 EDs and had at least one inhibitor test performed at or beyond this milestone. Additionally, any patient who develops an inhibitor following the initial rFVIII Fc

	Statistical Analysis Plan	Final v1.0
---	----------------------------------	-------------------

administration will be included in the numerator and denominator. Patients who do not develop an inhibitor but reached the milestone number of EDs will be included in the denominator, i.e.,:

$$\text{Incidence rate} = \frac{\text{Number of patients with an inhibitor}}{\text{Number of patients reaching ED milestone or who have an inhibitor}}$$

An exact 95% confidence interval for the proportion of patients with a positive inhibitor will be calculated using the Clopper-Pearson method for a binomial proportion. PROC FREQ in SAS version 9.4 or higher will be used to produce this confidence interval.

9.4.3.3. Supporting Analyses

To support the primary analysis results, the following will also be presented, using the primary methodology.

Overall Incidence based upon ED Milestones

The overall incidence of positive inhibitor formation will be presented for all patients who have reached at least 1, 20 and 50 EDs and had at least one inhibitor test performed at or beyond this milestone.

Incidence by Titer

The incidence of positive inhibitor formation will be analysed separately for the types of inhibitor specified in Sections 5.1.2.4 and 5.1.2.5, namely:

- Patients with high-titer inhibitors
- Patients with low-titer inhibitors that meet the clinically meaningful criteria
- Patients with high-titer inhibitors or low-titer inhibitors that meet the clinically meaningful criteria
- Patients with low-titer inhibitors that do not meet the clinically meaningful criteria

These analyses will all be based upon all patients with at least 1, 10, 20 and 50 EDs.

Time to Inhibitor Development

The cumulative incidence of inhibitors over time (EDs) will be estimated using the Kaplan-Meier method. This will be presented graphically for high and low titer (CS and NCS) inhibitors, as defined in Sections 5.1.2.4 and 5.1.2.5, as well as overall CS and overall. For patients who do not have an inhibitor, follow-up time will be censored at the last ED at the time of analysis.

Additionally a summary of EDs at time of inhibitor development will be provided, again for high and low titer (CS and NCS) inhibitors as well as overall CS and overall. This will include Kaplan-Meier estimates of cumulative incidence of inhibitor development at 10, 20 and 50 EDs.

Incidence by Peak Titer

The incidence rate of high and low titer inhibitor formation will be estimated and presented for peak titers, defined as the highest titer level detected during testing, dichotomized by:

- High titer, where peak titer ≥ 5.00 BU/mL
- Low titer, where peak titer ≥ 0.60 and < 5.00 BU/mL.

These analyses will be based upon all patients with at least 1, 10, 20 and 50 EDs.

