- A positive high titer inhibitor is defined as an inhibitor test and confirmatory test, both with results of ≥ 5.00 BU/mL.

Patients with discordant inhibitor test results (initial low titer result followed by high titer result or initial high titer result followed by low titer result) should have repeat inhibitor testing performed by the central laboratory from third separate sample, drawn at least 2 weeks after the previous sample.

- If 2 of 3 test results are < 5.00 BU/mL, the inhibitor is considered low titer.
- If 2 of 3 test results are ≥ 5.00 BU/mL, the inhibitor is considered high titer.

In either case, the date of the inhibitor is the date of the sample with the first positive test result.

	Statistical Analysis Plan	Final v1.0
---	----------------------------------	-------------------

If, as per the algorithm above, a patient is initially classified as having a low titer inhibitor which subsequently becomes high titer using the same rules, this patient may be re-classified as follows:

- If the patient’s inhibitor becomes high titer without a significant increase in dose, defined as a dose that more than doubles between the time of development of the low titer and high titer inhibitors, then the patient should be considered high titer for the entire inhibitor period
- If the patient’s inhibitor becomes high titer after a significant increase in dose, defined as a dose that more than doubles, or after the patient commences ITI, then the patient should be considered low titer for the entire inhibitor period

All analysis of, and derivations based upon, inhibitor test results are performed using the Nijmegen Inhibitor Fc assay test.

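### Titer-class inhibitor curves use Kaplan-Meier with no rule for patients whose inhibitor is of another class; some readings bias these curves slightly upward

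*SAP*

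**What the plan says.** SAP 9.4.3.3, under Time to Inhibitor Development, names one estimator: "The cumulative incidence of inhibitors over time (EDs) will be estimated using the Kaplan-Meier method". The curves are by class: "This will be presented graphically for high and low titer (CS and NCS) inhibitors", with two further curves for overall CS and for all inhibitors. A companion table gives "Kaplan-Meier estimates of cumulative incidence of inhibitor development at 10, 20 and 50 EDs". The only censoring rule is "For patients who do not have an inhibitor, follow-up time will be censored at the last ED at the time of analysis". No competing-risks estimator is named in either document.

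SAP 5.1.2.4 fixes the class. For a patient whose low-titer inhibitor later becomes high titer, there are two outcomes:

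- Without a more than doubled dose, "then the patient should be considered high titer for the entire inhibitor period".
- With a more than doubled dose, "or after the patient commences ITI, then the patient should be considered low titer for the entire inhibitor period".

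The onset date does not depend on the class. Where titers are discordant, "In either case, the date of the inhibitor is the date of the sample with the first positive test result"; otherwise it is the first positive sample that was later confirmed. SAP 5.1.2.5 then splits low titer by medical adjudication into clinically meaningful (CS) and not (NCS), and counts every high-titer inhibitor as clinically meaningful.

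**The concern.** Under these rules an inhibitor patient has one event, one date and one class. Once he is in one class he cannot have an event in another. For the high-titer curve, low-titer CS and NCS inhibitors are therefore competing events. The same holds for the other class curves, and low-titer NCS competes with overall CS. Only the all-inhibitor curve has no competing class.

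One minus Kaplan-Meier for a single class, with other-class patients censored at onset, treats those patients as if they could still have that class of event later. It does not estimate the proportion who develop that class.

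At stake is the description of the primary endpoint by class, above all high titer by EDs. Different programming choices would give different figures from the same data, and under some of them the class curves would not add up to the overall curve.

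**Working it through.** **Inputs.** The documents state no inhibitor rate, class split or Kaplan-Meier value, so there is no figure of the plan's to reproduce. Two quantities are assumed: *F*, the overall incidence by 50 EDs, and *s*, the share of inhibitors in the class of interest. SAP 3.3 supplies about 105 dosed patients and at least 90 reaching 50 EDs.

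**Formulas.** Assume the class-specific hazards are proportional over EDs.

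- True cumulative incidence of the class: *F* × *s*.
- One minus Kaplan-Meier, other classes censored at onset: 1 − (1 − *F*)^*s*.
- Other-class patients excluded, complete follow-up: *Fs* / (1 − *F*(1 − *s*)).

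**Results for a class with half the events (*s* = 0.5).**

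| *F* | True | Censored at onset | Excess (points) | Sum of two such curves |
|---|---|---|---|---|
| 20% | 10.0% | 1 − 0.80^0.5 = 10.6% | 0.6 | 21.1% against 20% |
| 30% | 15.0% | 1 − 0.70^0.5 = 16.3% | 1.3 | 32.7% against 30% |
| 40% | 20.0% | 1 − 0.60^0.5 = 22.5% | 2.5 | 45.1% against 40% |

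**Other splits.** The formula depends only on the share of the class, so it also serves for three classes. At *F* = 30%, a class with a quarter of the events gives 8.5% against 7.5%, and a class or combination with three quarters (overall CS, for example) gives 23.5% against 22.5%. Over *F* from 10% to 50% and *s* from 0.25 to 0.75, the excess runs from 0.1 to 4.3 points.

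**Three ways of handling other-class patients.** A simulation used 105 patients, onset mostly before 20 EDs, 14.3% leaving before 50 EDs (1 − 90/105, taken as an assumption), an equal split, and 600 runs per scenario. Mean estimates at 50 EDs for one class:

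| Method | *F* = 30% | *F* = 40% |
|---|---|---|
| Aalen-Johansen | 15.0% | 19.9% |
| Kaplan-Meier, followed to last ED | 15.0% | 19.9% |
| Same, half of them leaving just after onset | 15.6% | 20.9% |
| Kaplan-Meier, censored at onset | 16.3% | 22.4% |
| Kaplan-Meier, excluded | 17.7% | 24.8% |

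The exclusion figures agree with the formula: 0.15/0.85 = 17.6% and 0.20/0.80 = 25.0%.

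**Can other-class patients be followed to 50 EDs?** Often, yes. Protocol 10.2.5.2.1 lets low-titer patients continue on study at the Investigator's discretion, and SAP 3.1.2.3 has ITI dosed daily. Some will leave, because SAP 3.1.3 withdraws ITI-eligible patients who do not undergo or continue ITI.

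**Scale.** The Clopper-Pearson 95% interval for 15/100 is 8.6% to 23.5%, that is, 6.4 points below and 8.5 above the estimate. The excess at 30% is 1.3 points.

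**The case against.** A reader might infer that every planned curve overstates incidence, or that the plan's high-titer figure is biased upward as written. The text does not support that. Such a bias requires other-class patients to be censored at onset or dropped, and the SAP says neither. Its one censoring rule takes inhibitor-free patients to their last ED. A natural extension to a class curve takes patients without *that class* to their last ED, and then the excess is zero to about one point in the scenarios above. The all-inhibitor curve has no competing class on any reading. This part of the objection stands, so the bias must be stated conditionally.

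It is also fair that little depends on these curves. SAP 5.1 plans no hypothesis test. The primary analysis (SAP 9.4.3.2) is a proportion with an exact interval. SAP 9.4.3.3 also gives incidence by titer as binomial proportions at the ED milestones, which do not have this problem. That limits the consequence. It does not settle which of several figures the class curves will show.

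A further objection is that the classes do not truly compete, because a low-titer inhibitor can become high titer. That fails on the SAP's own rules: a converting patient is given one class for the whole inhibitor period, and the onset date stays at the first positive sample.

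**Conclusion.** The point holds as a gap in specification with a conditional bias. The SAP applies Kaplan-Meier to mutually exclusive classes and leaves open how other-class patients are treated. In the same assumed scenario (30% overall, equal split) the choice moves the 50-ED figure for one class from 15.0% to 16.3% or 17.7%. Where the bias arises it always runs upward, and a confidence interval does not reflect it. At overall incidences up to 40% and with censoring at onset, it is at most about 2.5 points, well inside sampling error.

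These sizes rest on assumed incidence, class shares, proportional class hazards, onset timing and withdrawal after onset, none of which the documents give. The effect is confined to the supporting class-specific curves and their 10, 20 and 50 ED estimates. The priority is low.

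**What to change.** In SAP 9.4.3.3, specify the Aalen-Johansen cumulative incidence function for the high-titer, low-titer CS, low-titer NCS and overall CS curves and for their estimates at 10, 20 and 50 EDs. Treat the remaining inhibitor classes as competing events, and continue to censor inhibitor-free patients at their last ED. Keep Kaplan-Meier for the all-inhibitor curve. The high-titer, low-titer CS and low-titer NCS curves then sum to the overall curve, and the question of how other-class patients enter is settled.

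The cost is a sentence or two in the SAP and a different procedure option in the same software. No new data are needed, and no other analysis changes.

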9.4.3.4. Additional Analyses

Patients with low titer inhibitors who remain in the main study may achieve remission without ITI. This is defined as negative inhibitor titers (< 0.60 BU/mL) in 2 consecutive determinations at least 28 days apart. These patients will be listed separately.

9.4.4. Incidence of Anti-FVIII Antibodies

The development of anti-rFVIII Fc [REDACTED] antibodies will be assessed as the number and percentage of patients negative throughout the study, at each study visit, at any time following treatment with rFVIII Fc, and at the final evaluation. Percentages will be based on the number of patients who are antibody negative prior to treatment with rFVIII Fc and have at least one post baseline antibody evaluation for the referenced time point or time interval.

Results from blood samples collected during surgical/rehabilitation periods for the purpose of determining the presence of anti-rFVIII Fc [REDACTED] antibodies will be included in this analysis.

In addition to a listing of all anti-rFVIII Fc [REDACTED] antibody results, a separate listing of all results from patients with at least one positive outcome during the study, including at baseline, will be provided.

9.5. Vital Signs

Vital signs include temperature, pulse, systolic and diastolic blood pressure, respiratory rate, pulse, temperature, height and weight. All vital signs except height and weight were measured prior to and approximately 20 minutes after each dose of rFVIII Fc. Height and weight were measured prior to dosing. Temperature was measured using the following methods: oral, rectal, tympanic, forehead, and axillary.

Vital signs will be summarized for the observed values and change from baseline using descriptive statistics for the Safety Analysis Set. Temperature measurements not taken by the same method pre and post dose will be excluded from the analysis with the exception of the combination of tympanic and rectal measurements. Evaluations taken during major surgical/rehabilitation periods will not be included in any summary.

A listing of all vital signs will be provided, including from unscheduled visits and during surgical/rehabilitation periods. Vital signs collected during surgical/rehabilitation periods as well as those occurring on the day of surgery will be flagged in this listing.

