### **16.5.2.3. Other Safety Parameters**

Clinical laboratory values will be summarized for change from baseline, shifts, and potentially clinically significant abnormalities. Threshold levels for potentially clinically significant laboratory abnormalities will be provided in the SAP. Listings of abnormal laboratory test results will be provided.

Vital signs will be summarized by the number and percentage of subjects with abnormalities. Abnormal values will be defined in the SAP. A listing of abnormal vital signs will be provided.

Duration of exposure and the total number of EDs to rFVIII Fc per subject will be summarized overall based on the Safety Analysis Set.

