5.3. Data Summaries

5.3.1. Continuous Variables

Continuous variables (e.g., age) will be summarized using the following standard summary statistics: number of patients (n), mean, standard deviation (SD), median, minimum value (min), and maximum value (max). In addition, if specified in the analysis table shells for this study, the 25th and 75th percentiles will also be presented. Summary statistics, excluding minimum and maximum, will be presented to one decimal place beyond that with which the study data were collected. For example, for data collected to no decimal place (e.g., 20 EDs), the mean and median will be presented to 1 decimal place and the SD to 2 decimal places; for data collected to 1 decimal place, the mean and median will be presented to 2 decimal places and the SD to 3 decimal places; and so forth. Minimum and maximum will be displayed as reported in the source data. If the measurements are transformed, then the mean, median, SD, minimum, maximum of the transformed measurements will be presented with the appropriate precision.

Unless impractical within a table of analysis results, statistics will be aligned by the decimal place in the summary tables (even if not displayed in this manner in the table shells).

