10. CHANGES TO PLANNED ANALYSIS

This SAP is based on Version 6 of the approved study protocol dated 12 February 2018. The major differences in the analysis described in this SAP compared to the protocol are:

- The Full Analysis Set consists of all patients who received at least 1 dose of rFVIIIIFc and were enrolled.
- An ITI Analysis Set and period was defined for the analysis of immune tolerance induction response data.
- The health outcomes questionnaire used in the study is not as specified in the protocol. The analysis described refers to that which was actually used and this can be found in [Appendix A](#)

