Summary of shifts from baseline to minimum/maximum post-baseline value for laboratory results: Hematology
Summary of potentially clinically significant laboratory abnormalities: Hematology
Summary of laboratory results and change from baseline for episodic and prophylactic regimens: Blood Chemistry
Summary of laboratory results and change from baseline for ITI regimen: Blood Chemistry
Shifts from baseline to minimum/maximum post-baseline value for laboratory results: Blood Chemistry

	Statistical Analysis Plan	Final v1.0
---	----------------------------------	-------------------

Summary of shifts from baseline to minimum/maximum post-baseline value for laboratory results: Blood Chemistry
Summary of potentially clinically significant laboratory abnormalities: Blood Chemistry
Inhibitors
Summary of inhibitor development by Nijmegen-modified Bethesda assay
Summary of peak titer inhibitor development by Nijmegen-modified Bethesda assay
Summary of time to inhibitor development
Other Safety
Summary of anti-rFVIII Fc antibodies
Summary of vital sign results and change from baseline for episodic and prophylactic regimens
Summary of vital sign results and change from baseline for ITI regimen

List of listings

Background/demography
Listing of lot numbers for study drug
Listing of protocol versions consented to
Listing of end of study disposition
Listing of demographic and baseline characteristics
Listing of caregiver’s demography
Listing of medical and surgical history
Listing of informed consent date and analysis populations
Listing of hemophilia history – diagnosis and diagnostic factors
Listing of Hemophilia history – bleeding history 3 months prior to screening
Listing of hemophilia history – pre-study FVIII treatment
Listing of risk factors
Listing of prior and concomitant medication taken through the end of study visit
Listing of concomitant medication taken after the end of study visit and prior to follow-up
Listing of maternal concomitant medication taken through the end of study visit
Listing of maternal concomitant medication taken after the end of study visit and prior to follow-up
Listing of other therapy or concomitant procedures
Listing of major and minor protocol deviations
Exposure/dosing
Listing of all injections and treated bleeding episodes
Listing of injections to treat a bleed
Listing of exposure
Listing of dose and consumption endpoints
Listing of prescribed dose and regimen changes
Listing of compliance endpoints
Efficacy

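### SAP 9.5 drops the protocol's count and listing of children with abnormal vital signs, sets no limits for abnormality, and does not declare the change

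*SAP*

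**What the plan says.** Protocol 16.5.2.3 fixes the form of the summary: "Vital signs will be summarized by the number and percentage of subjects with abnormalities". It then assigns the limits to the SAP and promises a listing: "Abnormal values will be defined in the SAP. A listing of abnormal vital signs will be provided".

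SAP 9.5 takes a different form: "Vital signs will be summarized for the observed values and change from baseline using descriptive statistics for the Safety Analysis Set". Its listing covers everything: "A listing of all vital signs will be provided, including from unscheduled visits and during surgical/rehabilitation periods". The only flags described for that listing mark records from surgical/rehabilitation periods and from the day of surgery.

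The output list in SAP Section 12 agrees with SAP 9.5. It has two vital-sign tables, "Summary of vital sign results and change from baseline for episodic and prophylactic regimens" and "Summary of vital sign results and change from baseline for ITI regimen", and one listing of measurements.

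SAP Section 10 opens with "The major differences in the analysis described in this SAP compared to the protocol are" and gives three items: the definition of the Full Analysis Set, the ITI analysis set and period, and the health outcomes questionnaire. Vital signs do not appear.

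**The concern.** The primary objective is safety. The protocol gives the risk of allergic reaction as the reason for observing the first doses (Sections 7.1 and 10.1), and it schedules vital signs before and about 20 minutes after injections given in clinic. It chose to report these data by counting children with abnormal values. The SAP describes distributions instead.

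The two are not interchangeable. The number of children beyond a limit cannot be recovered from a mean, standard deviation, median, minimum and maximum. It could be worked out later from the full listing, but only with limits chosen after the data have been seen, which is what fixing them in the SAP was meant to prevent. At stake is a promised safety result that would be missing from the study report, with no record of when or why it was dropped.

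**Working it through.** The plan states no figure here and there is nothing to recalculate. The check sets the documents side by side.

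**Step 1. Commitments against delivery.**

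| Protocol 16.5.2.3, vital signs | SAP |
|---|---|
| Count and percentage of children with abnormal values | Absent from 9.5 and from the Section 12 tables |
| Abnormal limits set in the SAP | None; Tables 2 and 3 cover hematology and chemistry only |
| Listing of abnormal values | Absent; one listing of all measurements, with no abnormality flag |

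Carried over: 0 of 3. Vital-sign tables planned: 2, neither of them a count of abnormal values. Departures declared in Section 10: 3, none on vital signs.

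**Step 2. Comparison with the laboratory data.** The same protocol section makes matching promises for laboratory values: clinically significant abnormalities, thresholds in the SAP, and a listing of abnormal results. The SAP keeps these. Section 9.4.1.3 gives thresholds and the number and percentage of patients beyond them, and Section 12 includes listings of abnormal hematology and chemistry values. Only the vital-sign half was lost. No reason is given, and nothing in the visible text suggests that a redaction explains the gap.

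**Step 3. What the SAP's summary can show.** SAP 5.3.1 defines the descriptive statistics for continuous data as the count, mean, standard deviation, median, minimum and maximum. The most extreme included value therefore appears, but the number of children who share it or come near it does not.

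**Step 4. What change from baseline means.** SAP 5.1.2.3 sets baseline as the last usable value before the first ever dose, unless stated otherwise, and SAP 9.5 states nothing else.
- *First dose.* The Baseline Incremental Recovery Visit schedules vital signs before and after dosing (Protocol 4.2.1). Where that visit gives the first dose, post-dose change from baseline is the same-visit change.
- *Later doses.* Children are under 6 at consent (Protocol 8.1) and take part for about 6 months to 3 years (Protocol 7.3). A post-dose value months later is compared with a baseline from a younger child, so ageing and dosing are mixed. The same applies to a child already dosed before the baseline recovery visit, since Protocol 7.1 allows up to 3 earlier doses.

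SAP 9.5 drops temperatures whose method differed before and after the dose, with one exception. This suggests that paired data are in view, but no same-visit difference is planned.

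**The case against.** The best defence is that little information is lost. Observed values are summarized as well as change, with minimum and maximum, and every measurement is listed, including those from unscheduled visits. An adverse event includes any unfavorable and unintended sign, and treatment-emergent events are tabulated by patient. Allergic reactions of Grade 2 or greater must be reported as serious and lead to withdrawal. Vital signs fall under other safety parameters in a descriptive study, and Section 10 claims to list only major differences.

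Much of this stands, and it rules out stronger readings. A reader might infer that the SAP leaves only averages that conceal individual children. It does not, because the extremes and the full listing remain. A reader might infer that change from baseline cannot show an acute reaction. It can at the first dose, when that dose is given at the baseline recovery visit. A reader might also infer that reactions go uncounted, but those that are recognised clinically are counted as adverse events.

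The defence does not restore the missing result. Adverse-event counts rest on the investigator's judgement and not on a limit, and the protocol planned both. The wording in Protocol 16.5 that lets the SAP specify otherwise concerns summarizing safety data overall. It does not cancel the instruction to define abnormal values. Even if the change is thought minor, removing the only vital-sign summary that the protocol names deserves a line in Section 10.

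**Conclusion.** The point holds as an undeclared inconsistency between protocol and SAP. Followed as written, the SAP omits a promised safety table, the limits it depends on, and the matching listing. No planned output would report how many children had an abnormal vital sign under limits set beforehand.

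The consequence is moderate. The primary endpoint and its analysis are untouched, and extremes and recognised reactions remain visible by other routes. The loss cannot be expressed as a number of children, because the documents contain no vital-sign data and no limits.

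The conclusion rests on the visible text of the two documents, and on the assumption that no vital-sign limits sit in a separate specification that the SAP does not cite for this purpose. The remark about ageing assumes only that normal vital signs shift with age in young children. The documents give no size for that shift, and none is needed for the main point.

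**What to change.** Before database lock:

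1. In SAP 9.5, define abnormal limits for the vital signs to be assessed. The sponsor's safety group should set them and make them suitable for the age range.
2. Add to SAP 9.5 and Section 12 a table of the number and percentage of children with abnormal values, and a listing of those values. The planned summaries of observed values and change can stay.
3. Optionally, add a same-visit summary of post-dose minus pre-dose values. Neither document requires it, but it would separate dosing from ageing after the first dose.

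If the sponsor intends to drop the protocol's analysis, it should declare and justify this in Section 10 instead.

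The cost is SAP wording, one table, one listing and the safety group's time to agree limits. The data are already collected, so no child needs a further procedure. Because SAP 3.5 applies the planned analyses to both the interim and the final analysis, the limits are best settled before vital signs are first tabulated.
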